8.2. Laboratory Test Abnormalities

Laboratory abnormalities that constitute an AE in their own right (considered clinically meaningful, induce clinical signs or symptoms, require concomitant therapy, or require changes in study drug) should be recorded on the Adverse Event form in the eCRF. Whenever possible, a diagnosis rather than a symptom should be provided (eg, "anemia" instead of "low hemoglobin"). Laboratory abnormalities that meet the criteria for AEs should be followed until they have returned to normal or an adequate explanation of the abnormality is found. When an abnormal laboratory test result corresponds to a sign or symptom of a previously reported AE, it is not necessary to separately record the laboratory test result as an additional event.

Laboratory abnormalities that do not meet the definition of an AE should not be reported as AEs. A Grade 3 or 4 AE does not automatically indicate an SAE unless it meets the definition of serious, as defined in Section 8.3.1. A dose modification for the laboratory abnormality may be required (see Section 5.4.1) and should not contribute to the designation of a laboratory test abnormality as an SAE.

8.3. Serious Adverse Events

8.3.1. Definitions

An SAE is defined as an event that meets at least 1 of the following criteria:

- Is fatal or life-threatening.
- Requires inpatient hospitalization or prolongation of existing hospitalization, unless hospitalization is a result of:
 - A routine treatment or monitoring of the studied indication not associated with any deterioration in condition.
 - An elective surgery or preplanned treatment for a pre-existing condition that is unrelated to the indication under study and has not worsened since signing the ICF.
 - A treatment on an emergency outpatient basis for an event not fulfilling any of the definitions of a SAE and not resulting in hospital admission.
 - Any social reasons and respite care, in the absence of any deterioration in the subject's general condition.
- Results in persistent or significant disability, incapacity, or a substantial disruption of a person's ability to conduct normal life functions.
- Constitutes a congenital anomaly or birth defect.
- Is considered to be an important medical event or a medically significant event that may not result in death, be immediately life-threatening, or require hospitalization but may be considered serious when, based on appropriate medical judgment, the event may jeopardize the subject or may require medical or surgical intervention to prevent 1 of the outcomes listed above.

8.3.2. Reporting

Every SAE, regardless of suspected causality (eg, relationship to study drugs or study procedure or disease progression), occurring after the subject has signed the ICF through the last study visit (or 30 days after the last dose of study drug, whichever is later) must be reported to the sponsor (or designee) within **24 hours** of learning of its occurrence, unless otherwise specified by the Protocol. Any SAEs occurring more than 30 days after the last dose of study drug should be reported to the sponsor or its designee only if the investigator suspects a causal relationship to the study treatment.

Information about all SAEs is collected and recorded on the Adverse Event form of the eCRF. The investigator must assess and record the causal relationship of each SAE to the study treatment.

The investigator must also complete the Incyte Serious Adverse Event Report Form, in English, and send the completed and signed form to the sponsor or designee within 24 hours of becoming aware of the SAE. The investigator must provide a causality assessment, that is, assess whether there is at least a reasonable possibility that the SAE is related to the study treatment: suspected (yes) or not suspected (no). Refer to the Incyte Reference Guide for Completing the Serious Adverse Event Report Form.

The contact information of the sponsor's study-specific representatives is listed in the investigator manual provided to each site. The original copy of the SAE Report Form and the confirmation sheet must be kept at the study site.

Investigational site personnel must report any new information regarding the SAE within 24 hours of becoming aware of the information in the same manner that the initial SAE Report Form was sent. Follow-up information is recorded on an amended or new SAE Report Form, with an indication that it is follow-up to the previously reported SAE and the date of the original report. The follow-up report should include information that was not provided on the previous SAE Report Form, such as the outcome of the event (eg, resolved or ongoing), treatment provided, action taken with study drug because of the SAE (eg, dose reduced, interrupted, or discontinued), or subject disposition (eg, continued or withdrew from study participation). Each recurrence, complication, or progression of the original event should be reported as follow-up to that event, regardless of when it occurs.

If the SAE is not documented in the RSI section of IB for the study drug (new occurrence) and is thought to be related to the sponsor's study drug, the sponsor or its designee may urgently require further information from the investigator for reporting to health authorities. The sponsor or its designee may need to issue an Investigator Notification (IN) to inform all investigators involved in any study with the same drug that this SAE has been reported. Suspected Unexpected Serious Adverse Reactions (SUSARs) will be collected and reported to the competent authorities and relevant ethics committees in accordance with Directive 2001/20/EC, or as per national regulatory requirements in participating countries.

8.4. Emergency Unblinding of Treatment Assignment

Not applicable.

8.5. Adverse Events of Special Interest

Specific AEs, or groups of AEs, will be followed as part of standard safety monitoring activities.

- $ALT \geq 5 \times ULN$
- $AST \geq 5 \times ULN$
- Colitis
- Diarrhea \geq Grade 2
- Rash \geq Grade 2
- Intestinal perforation
- Pneumonitis
- *Pneumocystis jirovecii* infection
- CMV infection
- Herpes simplex virus infection
- Varicella zoster virus infection
- Exfoliative dermatitis

8.6. Pregnancy

Pregnancy, in and of itself, is not regarded as an AE unless there is suspicion that study drug may have interfered with the effectiveness of a contraceptive medication or method. When a pregnancy has been confirmed in a subject during maternal or paternal exposure to study drug, the following procedures should be followed in order to ensure subject safety:

- The study drug must be discontinued immediately (female subjects only; see Section 5.4.1 for the maximum permitted duration of study drug interruption).
- The investigator must complete and submit the Incyte Clinical Trial Pregnancy form to the sponsor or its designee within **24 hours** of learning of the pregnancy.

Data on fetal outcome and breastfeeding are collected for regulatory reporting and drug safety evaluation. Follow-up should be conducted for each pregnancy to determine outcome, including spontaneous or voluntary termination, details of the birth, and the presence or absence of any birth defects, congenital abnormalities, or maternal and/or newborn complications, by following until the first well-baby visit. Pregnancy should be recorded on a Clinical Trial Pregnancy form and reported by the investigator to the sponsor or its designee. Pregnancy follow-up information should be recorded on the same form and should include an assessment of the possible causal relationship to the sponsor's study drug to any pregnancy outcome, as well as follow-up to the first well-baby visit or the duration specified in local regulations, whichever is later. Refer to the Incyte Reference Guide for Completing the Clinical Trial Pregnancy Form.

Any SAE occurring during pregnancy must be recorded on the SAE report form and submitted to the sponsor or designee.

8.7. Warnings and Precautions

Special warnings or precautions for the study drug, derived from safety information collected by the sponsor or its designee, are presented in the Investigator's Brochure (IB). Additional safety information collected between IB updates will be communicated in the form of Investigator Notifications (INs). Any important new safety information should be discussed with the subject during the study, as necessary. If new significant risks are identified, they will be added to the ICF.

8.8. Independent Data Monitoring Committee

An independent Data Monitoring Committee (IDMC) will be formed. The IDMC will consist of qualified individuals who are not involved with the conduct of the study. The establishment, composition, roles, duties, and responsibilities of the IDMC are addressed in the approved IDMC charter.

8.9. Product Complaints

The sponsor collects product complaints on study drugs and drug delivery systems used in clinical studies in order to ensure the safety of study participants, monitor quality, and facilitate process and product improvements.

All product complaints associated with material packaged, labeled, and released by the sponsor or its designee will be reported to the sponsor. All product complaints associated with other study material will be reported directly to the respective manufacturer.

The investigator or his/her designee is responsible for reporting a complete description of the product complaint via email or other written communication to the sponsor contact or respective manufacturer as noted in the packaging information. Any AE associated with a product complaint should be reported as described in Section 8.1.2 of this Protocol.

If the investigator is asked to return the product for investigation, he/she will return a copy of the product complaint communication with the product.

[figure not shown]
9. STATISTICS

Descriptive summaries for continuous variables will include, but not be limited to, the number of observations, mean, standard deviation, median, minimum, and maximum. Descriptive summaries for categorical variables will include the number and percentage of subjects in each category.

9.1. Study Populations

The full analysis set includes all subjects enrolled in the study who received at least 1 dose of INCB050465. The full analysis set will be used for the summary of demographics, baseline characteristics, subject disposition, and analyses of all efficacy data.

The safety population includes the same set of subjects as the full analysis set. This population will be used for all safety analyses.

9.2. Selection of Sample Size

Approximately 120 subjects will be enrolled and assigned to either treatment Group A or Group B. The first 50 subjects will be assigned at a 1:1 ratio to 2 treatment groups, and the remaining 70 subjects will be allocated to the selected treatment group based on the emerging safety and efficacy data from this and other monotherapy studies of INCB050465 in NHL that are evaluating the same or similar dosing regimens. If the true ORR is 51% for subjects in Group A and Group B, then with 120 total subjects, there is approximately 93% probability of observing the lower bound of the 95% confidence interval (CI) of $ORR \geq 35\%$.

9.3. Level of Significance

There will not be any statistical comparison between the 2 groups. Two-sided 95% CIs will be reported for all analyses when appropriate.

9.4. Statistical Analyses

9.4.1. Efficacy Analyses

9.4.1.1. Primary Efficacy Analyses

The primary endpoint ORR is the percentage of subjects with a CR or PR as defined by revised response criteria for lymphomas (Cheson et al 2014) per IRC. The ORR as determined by the IRC and its 95% exact binomial CIs will be calculated. Subjects whose baseline disease assessment or on-study response assessments cannot be adequately assessed for response will be considered as nonresponders. These subjects will be included in the denominators in the calculations of ORR.

The primary efficacy analyses will be conducted when all subjects in the full analysis set who have achieved a response (ie, PR or CR) according to the IRC have had approximately 12 months of follow-up from the onset of response.

Subgroups will be formed based on the following subject characteristics and baseline variables:

- Age: ≤ 65 years, > 65 years
- Gender: male, female
- Geographic region: Europe, North America, Rest of World

Subgroups may be further divided or combined based on emerging data. The ORR and its 95% CIs will be provided for each subgroup. A forest plot will be created to summarize the variability in ORRs across subgroups.

9.4.1.2. Secondary Efficacy Analyses

Complete response rate is the percentage of subjects with a CR as defined by revised response criteria for lymphomas, as determined by an IRC. The CRR determined by the IRC and its 95% exact binomial CIs will be calculated.

Duration of response is defined as the time from first documented evidence of CR or PR until disease progression or death due to any cause among subjects who achieve an overall response, as determined by IRC. For subjects who have not progressed and are still alive at the time of the analysis, DOR will be censored on the day of last evaluable disease assessment. For subjects who have discontinued study or have started other anticancer treatment, DOR will be censored on the day of last evaluable disease assessment documenting absence of PD before the discontinuation or the start of the new anticancer treatment. Kaplan-Meier estimation of median DOR per IRC and its 95% CIs will be provided.

Progression-free survival is defined as the time from the date of the first dose of study drug to the first documented disease progression as determined by IRC, or death due to any cause, whichever occurs first. For subjects who have not progressed and are still alive at the time of the analysis, PFS will be censored on the day of last evaluable disease assessment. For subjects who have discontinued study or have started other anticancer treatment, PFS will be censored on the day of last evaluable disease assessment documenting absence of PD before the discontinuation or the start of the new anticancer treatment. For subjects who have no baseline or no postbaseline disease assessment, PFS will be censored with censored duration of 1 day. Kaplan-Meier estimation of median PFS per IRC and its 95% CIs will be provided.

Overall survival is defined as the time from the date of the first dose of study drug to death due to any cause. For subjects who are still alive at the time of the analysis, OS will be censored on the date the subject is last known to be alive. The Kaplan-Meier estimation of median OS and its 95% CIs will be provided.

For subjects with measurable lesions at baseline, target lesion sizes will be measured by sum of the product of the diameters of all target lesions. The best percentage change from baseline, defined as the largest decrease in target lesion sizes during the study, will be summarized descriptively. Note that for subjects who only have increases in target lesion sizes from baseline, the smallest increase will be considered as the best change from baseline. Target lesions considered "too small to measure" will be assigned a default value of 5 mm \times 5 mm for purposes

of this analysis. Likewise, target lesions identified as "not present" at postbaseline assessments will be assigned 0 mm for this analysis. In the event that a target lesion is unaccounted for in a particular postbaseline timepoint (ie, the assessment is missing or NE), then the overall sum of target lesions will not be evaluable for that postbaseline timepoint.

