2. STUDY OBJECTIVES AND ENDPOINTS

The study objectives and endpoints are presented in [Table 1](#).

Table 1: Objectives and Endpoints

Objectives	Endpoints
Primary	
To assess the efficacy of INCB050465 in terms of ORR in subjects with relapsed or refractory FL.	ORR defined as the percentage of subjects with a CR or PR as defined by revised response criteria for lymphomas, as determined by an IRC.
Secondary	
To assess CRR.	CRR defined as the percentage of subjects with a CR as defined by revised response criteria for lymphomas (Cheson et al 2014), as determined by an IRC.
To assess DOR.	DOR defined as the time from first documented evidence of CR or PR until disease progression or death from any cause among subjects who achieve an objective response, as determined by radiographic disease assessment provided by an IRC.
To assess PFS.	PFS defined as the time from the date of the first dose of study treatment until the earliest date of disease progression, as determined by radiographic disease assessment provided by an IRC, or death from any cause.
To assess OS.	OS defined as the time from the date of the first dose of study treatment until death from any cause.
To assess best percentage change in target lesion size.	Best percentage change in target lesion size from baseline, where target lesion size is measured by the sum of the product of the diameters of all target lesion sizes.
To characterize the safety and tolerability of INCB050465.	Safety measured by clinical assessments, including vital signs and physical examinations, 12-lead ECGs, chemistry and hematology laboratory values, and AEs.

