#### 7.4.3. Progression-Free Survival

Progression-free survival is defined as the time from the date of the first dose of the study drug to the first documented disease progression as determined by revised response criteria for lymphomas (Cheson et al 2014), or death due to any cause, whichever occurs first. For responses assessed by IRC, date of disease progression will be provided by the Clinical Reviewer. Censoring for PFS will follow the algorithm outlined in Table 2, which is based on FDA Guidance for Industry: Clinical Trial Endpoints for the Approval of Non-Small Cell Lung

Cancer Drugs and Biologics (2015) and Guidance for Industry: Clinical Trial Endpoints for the Approval of Cancer Drugs and Biologics (2018).

Table 2: Evaluation and Censoring of Progression-Free Survival

Situation	Outcome	Date of Progression or Censoring
No baseline tumor assessments	Censored	Day 1
No valid postbaseline response assessments	Censored	Day 1
Progression documented between scheduled response assessments	Progressed	Date of first overall response of PD
No progression	Censored	Date of last valid radiologic assessment (not NE and not missing)
Study discontinuation for undocumented progression	Censored	Date of last valid radiologic assessment (not NE and not missing)
Study discontinuation for toxicity or other reason	Censored	Date of last valid radiologic assessment (not NE and not missing)
New anticancer treatment started	Censored	Date of last valid radiologic assessment (not NE and not missing) on/before starting a new anticancer treatment
Death before first progressive response assessment	Progressed	Date of death
Death between adequate response assessments	Progressed	Date of death
Death or progression after two or more missed assessments	Censored	Date of last valid radiologic assessment (not NE and not missing) before the missed assessments

NE = not evaluable.

The number of participants whose disease progressed per the IRC or who died, and the number of participants censored will be summarized by treatment groups and combined. The Kaplan-Meier estimate of median PFS as determined by the IRC will be presented with its 95% CIs, with the CIs calculated using the generalization of Brookmeyer and Crowley's method (1982) with log-log transformation (Klein and Moeschberger 1997). Progression-free survival rates at 6, 12, 18, 24, and 36 months will also be provided with 95% CIs calculated using Greenwood's formula to estimate the standard error.

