# 11.1. Changes to Protocol-Defined Analyses

The PP population was removed from the planned analysis. For a single-arm, open-label study, the determination of participants to be excluded from the PP population is post hoc and may not be done objectively; thus, analysis based on this population may not be meaningful.

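### A death before the first scan is both a PFS event and a Day 1 censoring under the plan's rules, with no order of precedence

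*Protocol*

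**What the plan says.** Protocol Section 2 (Table 1) runs PFS from first dose to disease progression "as determined by radiographic disease assessment provided by an IRC, or death from any cause". Protocol 9.4.1.2 repeats that definition and adds three censoring sentences:

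- Subjects who "have not progressed and are still alive at the time of the analysis, PFS will be censored" are censored at the last evaluable disease assessment.
- Subjects who leave the study or start other anticancer treatment are censored at the last progression-free assessment before that point.
- "For subjects who have no baseline or no postbaseline disease assessment, PFS will be censored with censored duration of 1 day".

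SAP 7.4.3 hands PFS censoring to Table 2. Four of its rows matter here:

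- "No valid postbaseline response assessments": censored, Day 1. A companion row treats a missing baseline assessment the same way.
- "Death before first progressive response assessment": event, date of death.
- "Death or progression after two or more missed assessments": censored at the last valid assessment before the gap.

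Neither the table, its footnote nor the surrounding text ranks the rows. The first post-baseline scan is due at Week 8 (Protocol Table 6; SAP 7.2). SAP 11.1 declares one departure from the protocol: "The PP population was removed from the planned analysis".

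**The concern.** A subject who is dosed and dies before any valid scan belongs to the full analysis set and has had a PFS event by definition. The protocol's 1-day sentence nevertheless censors that subject, and Table 2 supports either outcome. The two readings give different event counts, medians and rates at 6, 12, 18, 24 and 36 months. The Day 1 reading is informative censoring: it removes the worst outcomes from the curve.

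The case is foreseeable. The interim trigger (Protocol 9.6, SAP Section 10) already provides for subjects who stop treatment because of death, and SAP 9.2.3 plans a fatal-event summary for the initial daily-dosing period, planned as 8 weeks. A death could appear in that summary while PFS shows the same subject as censored at Day 1.

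The event and censoring counts are also split by regimen: "the number of participants censored will be summarized by treatment groups and combined". A single early death weighs most in the non-selected group, planned at about 25.

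**Working it through.** **1. The rules applied to one subject.** Take a subject with a valid baseline scan who dies before Week 8, never scanned on study.

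- Protocol definition: event on the date of death.
- Protocol 1-day sentence: no post-baseline assessment, so censored at 1 day. The condition of being alive, present in the first censoring sentence, is absent.
- Table 2, no-valid-assessment row: censored, Day 1.
- Table 2, death row: event, date of death.

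The same clash arises for a subject with no baseline assessment who dies. It also appears to arise for a subject whose only scan was not evaluable and who dies before Week 16, because Table 2 describes a valid assessment as neither missing nor not evaluable.

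The missed-assessments row overlaps as well. A never-scanned subject who dies after missing the Week 8 and Week 16 scans meets it, but there is no post-baseline assessment at which to censor.

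**2. Effect on the Kaplan-Meier curve.** The plan states no PFS figure to reproduce. Suppose k of N subjects die unscanned, before any other event or censoring.

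- Counted as events: the curve falls to (N−k)/N and continues with N−k at risk.
- Censored at Day 1: the curve stays at 1 and continues with the same N−k at risk.

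Hence S_Day1(t) = S_event(t) × N/(N−k) at every later time.

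**3. Numbers.** Planned sizes: 120 combined; 50/2 = 25 in the non-selected group; 25 + 70 = 95 in the selected group. Assumptions: k = 1 or 2, and a true landmark PFS of 75%. For scale, the simple 95% half-width is 1.96 × √(0.75 × 0.25/N).

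| N | k | Calculation | Day 1 result | Shift (points) | Half-width (points) |
|---|---|---|---|---|---|
| 120 | 1 | 0.75 × 120/119 | 75.6% | +0.6 | 7.7 |
| 120 | 2 | 0.75 × 120/118 | 76.3% | +1.3 | 7.7 |
| 95 | 1 | 0.75 × 95/94 | 75.8% | +0.8 | 8.7 |
| 95 | 2 | 0.75 × 95/93 | 76.6% | +1.6 | 8.7 |
| 25 | 1 | 0.75 × 25/24 | 78.1% | +3.1 | 17.0 |
| 25 | 2 | 0.75 × 25/23 | 81.5% | +6.5 | 17.0 |

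**4. Medians.** These come from a direct Kaplan-Meier calculation, with an assumed median near 15 months, exponential event times after Week 8 and no other censoring.

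| N | k | Day 1 censoring (months) | Death as event (months) |
|---|---|---|---|
| 120 | 3 | 15.0 | 14.7 |
| 120 | 6 | 15.2 | 14.2 |
| 25 | 1 | 15.8 | 14.2 |

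**The case against.** The best defence is that the intent is clear. In the protocol, the 1-day sentence can be read as completing the rule for living subjects by supplying a date when there is no last assessment. The middle censoring sentence lacks the alive condition too, and Protocol 5.7 lists death as a reason for study discontinuation. Read equally literally, that sentence would censor every death, which cannot be meant. In Table 2, the row naming death is the more specific one and agrees with the definition. On that reading Table 2 departs from nothing, and SAP 11.1 has nothing to declare.

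This shows what was probably intended, and it supports the fix. It does not supply the missing rule: the protocol sentence still points the other way, and a prespecified algorithm should not need interpretation once outcomes are known. The 11.1 point is secondary; it bites only if the protocol sentence is left as it stands.

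The points on size are fair. Eligibility requires a life expectancy of at least 12 weeks, so k is probably small. Two unscanned deaths among 25 would be 8%. Under SAP 5.2, subjects who cross over by the start of maintenance move to the selected group, so 25 and 95 are planned rather than final sizes. No between-group comparison is planned, and the listings of PFS and of deaths would let a reader find any affected subject.

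**Conclusion.** The rule is wrong as written. The protocol's 1-day sentence contradicts the PFS definition in its own paragraph, and Table 2 assigns one subject two opposite outcomes without ranking them. The error, if made, can only raise PFS. For one or two early deaths it is small in the combined analysis and a few points in a group of 25, within the sampling error in every case shown. These sizes rest on the assumed k and 75%, and on the early deaths preceding any other event or censoring.

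The reach is limited to PFS, a secondary descriptive endpoint that no decision rule uses. ORR and CRR keep unassessed subjects in the denominator, DOR covers responders only, and OS and the fatal-event tables still show the deaths. It should be corrected, but the primary conclusion does not depend on it.

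**What to change.** Add a footnote to SAP Table 2 with three statements:

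- The death rows take precedence over the two Day 1 censoring rows. A death with no valid assessment is an event on the date of death, unless the existing row for two or more missed assessments applies.
- For a never-scanned subject, that row applies only when the Week 8 and Week 16 scans have both been missed before death. The censoring date is then Day 1. Table 2 gives no date for this combination, so one has to be stated. This keeps the existing missed-assessments rule, and with it Day 1 censoring for those later deaths.
- Day 1 censoring otherwise stays for subjects with no valid assessment and no recorded death.

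Add the same exception for death to the 1-day sentence in Protocol 9.4.1.2, or record the departure in SAP 11.1.

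The cost is one footnote and one clause or line, with no new data. The PFS estimate may become slightly less favourable.
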